#### Visceral lesions:

F-DCFPyL positive visceral lesions will be considered. Visceral lesions (non-lymph node soft tissue or organ) will be assessed by change in size.

#### True positive:

 For patients undergoing systemic treatment (alone or in combination with targeted treatment): If on post-treatment follow-up imaging within 3-12 months, lesions seen on CT or MRI decrease by more than 30% in long axis diameter and PSA declines by more than 50%.

- If PSA increases by more than 50% on systemic therapy, then a increase in the size of lesion by more than 20% will be considered a true positive lesion.
- 2) In subjects with localized suspected lesions(s) receiving targeted treatment without concomitant systemic treatment there are two ways to meet true positive disease:
  - If the subject demonstrates a decrease of PSA by greater than 50% after targeted treatment [OR]
  - If on post-treatment follow-up imaging within 3-12 months, lesions seen on CT or MRI decrease by more than 30% in long axis diameter (with a minimum of 3 mm in change in size)
- 3) For untreated patients: If on follow-up imaging within 3-12 months, lesions seen on CT or MRI increase by more than 20% in long axis diameter (with a minimum of 3 mm in change in size).

#### False positive

- For patients undergoing systemic treatment (alone or in combination with targeted treatment): If on post-treatment follow-up imaging within 3-12 months, lesions seen on CT or MRI increase by more than 20% in long axis diameter and PSA decreases by more than 50%.
- 2) In subjects with localized suspected lesions(s) receiving targeted treatment without concomitant systemic treatment there are two ways to meet false positive disease:
  - If the subject does not demonstrate a decrease of PSA by greater than 50% after targeted treatment [OR]
  - If on post-treatment follow-up imaging within 3-12 months, lesions seen on CT or MRI increase by more than 20% in long axis diameter (with a minimum of 3 mm in change in size).
- 3) For untreated patients: If on follow-up imaging within 3-12 months, lesions seen on CT or MRI decrease by more than 30% in long axis diameter (with a minimum of 3 mm in change in size).

If all regions in a patient/region do not meet criteria for either True positive or False positive disease, then the patient/region will be considered unevaluable for primary endpoint.

# **Bone lesions**

F-DCFPyL positive bone lesions will be considered.

#### True positive:

- 1) If there was a corresponding positive sclerotic lesion on the CT portion of the  $^{68}$ Ga- $^{18}$ F-DCFPyL PET or on a separate CT obtained  $\leq$  30 days before or after the PET/CT in the same location as the PSMA uptake.
- 2) If there is focal uptake seen in the same location as the PSMA uptake on the baseline bone scan performed within one month of F-DCFPyL PET.
- 3) If there is a lesion noted in the same location as the PSMA uptake on the initial MRI performed within one month of F-DCFPyL.

- 4) If within 12 months follow-up CT demonstrates development of sclerosis in the same location as the PSMA uptake.
- 5) If within 12 months follow-up MRI demonstrates a new bone lesion in the same location as the PSMA uptake.
- 6) If within 12 months follow-up bone scan demonstrates new focal uptake in the same location as the PSMA uptake.
- 7) In subjects with localized suspected bone lesion(s) receiving targeted treatment without concomitant systemic treatment:
  - If the subject demonstrates a decrease of PSA by greater than 50% after targeted treatment.

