# 1.1.7.3 Analysis:

- PET/CT Images will be reviewed and analyzed using Siemens Syngo/TrueD workstation and Oasis workstation by a board-certified nuclear medicine physician experienced in reading PET/CT.
- 2. A molecular imaging TNM (miTNM) framework for F-DCFPyL PET/CT prostate cancer staging will be used (described in 2.3.8 Analysis Specifics).

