# Regional nodes (N) and distant metastases (M) miN1 miN2 miM1a miM1c miM1b (uni) miM1b (oligo) miM1b (diss) miM1b (dmi)

Figure 5: miTNM categories and pattern of pelvic nodal, distant metastases and bone involvement for reporting prostate cancer stage by F-DCFPyL PET/CT. Tumor involvement is delineated in red. Abbreviations: uni, unifocal; oligo, oligometastatic; diss, disseminated; dmi, diffuse marrow involvement.

In patients with organ involvement (miM1c) all involved organs need to be specified in the final report.

Probability of bone or organ involvement increases with focal uptake, higher PSMA expression score and/or CT/MRI abnormalities. For bone metastases common CT findings include sclerotic, rarely lytic lesions with or without extraosseous extension; common MRI findings include low signal on unenhanced T1 images.

PSMA-positive pitfalls such post-traumatic rib uptake, or non-prostate cancer related primary malignancies have to be ruled out (Rauscher et al., 2016).

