# Table 10: Level of certainty.

Certainty will substantially vary depending on uptake, location and CT or MRI findings. For instance at biochemical recurrence certainty of tumor localization will be substantially higher in case of focal uptake at a common location (e.g. internal iliac lymph node) as compared to an uncommon location (e.g. rib).

Standardized wording for level of certainty will improve communication between the reader and the treating physician.

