# False positive:

- 1) In subjects with localized suspected bone lesion(s) receiving targeted treatment without concomitant systemic treatment:
  - If the subject does not demonstrate a decrease of PSA by greater than 50% after targeted treatment with curative intent (ie non-palliative radiation).
- 2) If F-DCFPyL positive bone lesions do not meet the criteria for true positive findings, and appropriate correlative and follow-up imaging was acquired.

If bone lesions do not meet criteria for either true positive or false positive disease listed above, then the patient/region will be considered unevaluable for primary endpoint.

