#### 1) Patient level evaluation:

- a) *True positive patient*: A single region in a patient contains a true positive node either by pathology or imaging/clinical follow-up.
  - i) For a patient to be considered a True Positive, only one region is required to have a true positive lesion as described above, unless one region is categorized as a false positive based on pathology. This means that a single pathology false positive region outweighs regions with imaging/clinical follow-up true positive disease.
  - ii) A patient will be considered a True Positive if one region contains a lesion that is True Positive, even if other regions are categorized as inevaluable or false positive based on imaging or clinical follow-up.

- b) *True negative patient*: in the absence of True Positive or False Positive lesions, a patient will be considered a True Negative if there is pathology that is negative for disease and corresponding lesion is negative by F-DCFPyL PET.
- c) False positive patient:
  - i) Pathology confirms a false positive lesion that is read as positive on F-DCFPyL PET.
  - ii) In the absence of pathology: there are no true positive regions, and there is a region that is categorized as false positive based on imaging or clinical follow-up.
- d) False negative patient: in the absence of True Positive or False Positive lesions, a patient will be considered a False Negative if there is pathology that is positive for disease and corresponding lesion is negative by F-DCFPyL PET.
- 2) Region level evaluation: Each patient will have four evaluable regions (Table 1: prostate bed, pelvis, extrapelvic soft tissue, and bone metastases). Each region will be categorized as true positive or false positive as described above. Regions without evidence of F-DCFPyL positive disease or deemed unevaluable will not be included in the analysis.
  - a) True positive region:
    - i) Pathology confirms a F-DCFPyL avid lesion as a true positive in the region. ii) In the absence of pathology, clinical or imaging follow-up demonstrates a true positive lesion within the region independent of the presence of an inevaluable lesion or a false positive lesion (ie true positive disease will supersede a false positive lesion in the region based analysis if based on imaging/clinical follow-up).

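### Bone-lesion PPV is open to incorporation bias where sclerosis on the index PET/CT's own CT is the only confirmation

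*Combined protocol and SAP*

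**What the plan says.** Section 1.1.8.4, part 2) A), gives seven routes by which a PET-positive bone lesion becomes a true positive. The first begins "If there was a corresponding positive sclerotic lesion on the CT portion of the" PET itself. The alternative inside the same criterion, joined by or, is a separate CT no more than "30 days before or after the PET/CT in the same location as the PSMA uptake". The other six are a baseline bone scan, a baseline MRI, new findings within 12 months on CT, MRI or bone scan, and a PSA fall of more than 50% after targeted treatment alone.

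The reading framework in section 1.1.8.2 D) states: "Probability of bone or organ involvement increases with focal uptake, higher PSMA expression score and/or CT/MRI abnormalities". It adds: "For bone metastases common CT findings include sclerotic, rarely lytic lesions with or without extraosseous extension". Under E) it says of the reader's confidence: "Certainty will substantially vary depending on uptake, location and CT or MRI findings". On what the reader sees, section 1.1.7.3 says: "PET/CT Images will be reviewed and analyzed using Siemens Syngo/TrueD workstation and Oasis workstation by a board-certified nuclear medicine physician".

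The endpoint is worded differently. Secondary endpoint 2 in section 1.1.3.3 rests PPV on histopathology, biopsy or follow-up, and section 1.1.9.5 on pathology plus clinical and conventional-imaging follow-up. Section 1.1.9.5 asks for Wilson 95% intervals, separately for three blinded readers.

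Three further rules bear on the point. Bone false-positive rule 2 applies only if "positive bone lesions do not meet the criteria for true positive findings, and appropriate correlative and follow-up imaging was acquired". At region level, "true positive disease will supersede a false positive lesion in the region based analysis if based on imaging/clinical follow-up". At patient level, one true-positive region is enough unless pathology shows a false-positive region. Pathology ranks above imaging throughout.

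**The concern.** PPV should say how often a positive index scan is borne out by other evidence. Criterion 1 lets part of the index scan serve as that evidence, and the part it uses is a finding the reading framework offers the reader as a reason to suspect bone disease. This is incorporation bias. A lesion confirmed only in this way is counted as correct whatever its true nature, unless pathology contradicts it. The planned confidence intervals describe sampling error and do not reflect this.

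At stake are the bone-region PPV and, where bone is a patient's only true-positive region, the per-patient PPV. The management-change primary endpoint is not touched.

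**Working it through.** The plan states no figure on this point, so there is nothing to reproduce. The check sets the rules side by side and then works out the possible size.

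**Step 1: is there overlap?** The reading framework names sclerosis as a common CT finding in bone metastasis and lets CT abnormality raise both probability and certainty. Criterion 1 accepts sclerosis on the same CT, at the site of uptake, as confirmation. No section specifies a PET-only read, says the blinded readers are kept from the CT component, or gives the index CT to a separate reader. The overlap is therefore possible under the plan as written.

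**Step 2: does the endpoint wording cover it?** Sclerosis on the index CT is neither pathology nor follow-up. The imaging and clinical true-positive criteria for nodes, visceral lesions and prostate all rest on later size change or PSA response. Bone criterion 1 is the only route that can be met from the index scan itself.

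**Step 3: is it carried forward?** Yes. Meeting criterion 1 closes off bone false-positive rule 2. At region level the imaging true positive outranks imaging or clinical false positives, and a single true-positive region normally makes the patient true positive.

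**Step 4: how large could it be?** Let s be the share of evaluable PET-positive bone lesions (or regions, for per-region PPV) that are true positive only through index-CT sclerosis, q the share of those that are truly malignant, and p the PPV in the rest, taken as correctly classified.

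- PPV as defined = s + (1 − s)p
- Underlying PPV = sq + (1 − s)p
- Inflation = s(1 − q), which does not depend on p

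The documents give none of the three. Assuming p = 0.70:

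| s | PPV as defined | Underlying PPV at q = 0.9 / 0.8 / 0.7 | Inflation, points |
|---|---|---|---|
| 0.2 | 0.2 + 0.8 × 0.70 = 0.76 | 0.74 / 0.72 / 0.70 | 2 / 4 / 6 |
| 0.4 | 0.4 + 0.6 × 0.70 = 0.82 | 0.78 / 0.74 / 0.70 | 4 / 8 / 12 |
| 0.6 | 0.6 + 0.4 × 0.70 = 0.88 | 0.82 / 0.76 / 0.70 | 6 / 12 / 18 |

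If q = 1 the inflation is zero. Since q cannot exceed 1, this component is never downward.

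**Step 5: what would a PPV without these lesions estimate?** It estimates p, which differs from the underlying PPV by s(q − p). With s = 0.4 and q = 0.9 that is 0.4 × (0.9 − 0.7) = 0.08. The underlying value is 0.78, the PPV as defined is 0.82 (4 points high) and the restricted PPV is 0.70 (8 points low). If q is at least p, the two estimates bracket the underlying value.

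**The case against.** The strongest reply is that criterion 1 is a sensible part of a composite standard. Section 1.1.8.4 B) notes the high false-negative rate of bone biopsy, and sclerosis at a site of uptake is real evidence of metastasis. The reading text speaks of probability and certainty and sets no threshold for a positive call. The bone criteria apply to lesions already positive for the tracer, and the expression score depends on uptake alone. Sclerosis is thus not required for a positive read, and the plan does not show that it decides one. This stands, and it limits the point to being open to bias.

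Three stronger readings are tempting, and the documents do not support them.

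- A reader might infer that every PET-positive lesion with sclerosis is settled as true positive with nothing else able to count. Pathology outranks imaging, a biopsy showing Paget's disease makes the lesion a false positive, and readers must rule out pitfalls such as post-traumatic rib uptake. False-positive rule 1, on PSA after curative-intent targeted treatment, does not depend on failing the true-positive criteria. Many sclerotic lesions may also meet another criterion, and those are unaffected.
- A reader might infer that bone PPV then tracks the share of sclerotic lesions rather than accuracy. That would need sclerosis to carry no information, and section 1.1.8.2 D) says it does.
- A reader might take the gap between the PPV as defined and the PPV in the other lesions as the bias. That gap is s(1 − p), or 6 to 18 points in the table. It equals the inflation only if q = p, whereas the plan's own text suggests that q is higher.

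It is also fair to say that this concerns one of four regions of a secondary endpoint, although the bone text refers to lesions as unevaluable for the primary endpoint.

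**Conclusion.** The point holds in a limited form. For bone lesions confirmed only by sclerosis on the index CT, the plan lets one finding support both the positive call and its confirmation, and the confirmation is not of the kind the endpoint names. Bone-region PPV, and per-patient PPV where it depends on such a region, may be overstated.

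The inflation is s(1 − q): 2 to 18 points under the assumed s of 0.2–0.6 and q of 0.7–0.9, and none if q = 1. Those ranges are illustrative, and the documents cannot narrow them. Per-patient inflation follows the same formula with s counted in patients, and it is smaller where few patients depend on bone alone. The primary endpoint is unaffected. The matter is minor, but unless the confirming criterion is recorded nobody can tell afterwards which end of the range applies.

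**What to change.** Remove no criterion. Add one data field that records every criterion met by each PET-positive bone lesion, and for criterion 1 whether the sclerosis was on the index CT or a separate one. Then report bone-region and per-patient PPV in three rows:

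1. As defined.
2. With lesions confirmed only by index-CT sclerosis treated as unevaluable. State explicitly that they do not pass to false-positive rule 2, which would otherwise count some of them as errors.
3. As row 2, also leaving out lesions confirmed only by sclerosis on a separate CT within 30 days, because that CT shows the same finding.

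Present rows 2 and 3 as conservative sensitivity estimates beside row 1, not as the unbiased value. A lesion that is already sclerotic cannot meet criterion 4, which needs sclerosis to develop, while rule 2 false positives stay in the denominator. The restricted PPV can therefore be too low.

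The cost is one field and two rows per table. The drawbacks are fewer evaluable lesions, hence wider intervals, and that possible downward bias.

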# B) HISTOPATHOLOGY/BIOPSY:

Localization of lesions for histopathology/biopsy will be a classified by regions as specified in the miTNM framework. F-DCFPyL positive findings are aimed to be confirmed by histopathology (HP)/biopsy if clinically feasible. Pathology performed 60 days before the F-DCFPyL PET will be available for correlation. Histopathological procedures, biopsies and follow-up imaging will be performed as clinically indicated and as per institutional protocol.

The following elective procedures may guide the investigator:

Positive HP/Biopsy: Confirmed sites of metastatic or tumor involvement by histopathology/biopsy will be discussed with the responsible physician/surgeon.

- a) *True Positive*: lesion is positive on targeted biopsy/surgical sampling and is read as positive on F-DCFPvL PET.
- b) False Negative: lesion is positive on targeted biopsy/surgical sampling and is read as negative on F-DCFPyL PET.

Negative HP/Biopsy: Patients with suspected tumor recurrence on F-DCFPyL PET with negative histopathology/biopsy will be handled as outlined below:

- 1) Lymph nodes:
  - i) For patients undergoing nodal dissection: Patients will be rescanned with dedicated CT, MRI or a repeat F-DCFPyL PET to determine if the suspicious F-DCFPyL positive node was removed.
    - (1) If F-DCFPyL positive lymph node is still present, a repeat biopsy can be pursued if clinically feasible and applicable, or follow-up using imaging as described above will be performed.
    - (2) If the corresponding node was removed, then this will be considered a False Positive.

- ii) For patients undergoing needle biopsy: Images of the procedure will be reviewed to determine if the correct node was biopsied.
  - (1) If the correct node was biopsied, then a negative biopsy will be considered a False Positive.
  - (2) If the incorrect node was biopsied, then follow-up imaging as described above will be performed.
- 2) Bone lesions: Given the high rate of false negative biopsies for osseous metastases in patients with prostate cancer, patients with negative bone biopsies of PSMA PET positive lesions will be further evaluated:
  - a) If pathology demonstrates an alternative diagnoses that is known to be PSMA positive (eg Renal Cell Carcinoma metastases, Paget's disease), then this will be considered a False Positive.

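### Bone true-positive rules 1 to 3 do not require the baseline correlate to look like metastasis, so an unbiopsied PET-positive mimic can be scored as confirmed disease

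*Combined protocol and SAP*

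**What the plan says.** Section 1.1.8.4, part 2) A), Bone lesions, lists seven ways for a PET-positive bone lesion to be true positive. Three use baseline imaging:

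- Rule 1: a sclerotic lesion at the PET site, on the CT part of the PET/CT or on a separate CT within 30 days.
- Rule 2: "If there is focal uptake seen in the same location as the PSMA uptake on the baseline bone scan", where that scan was done within one month of the PET scan.
- Rule 3: "If there is a lesion noted in the same location as the PSMA uptake on the initial MRI performed within one month of" the PET scan.

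Rules 4 to 6 use follow-up imaging and need something that has changed. Rule 4, for example, reads "If within 12 months follow-up CT demonstrates development of sclerosis in the same location as the PSMA uptake"; rules 5 and 6 need a new MRI lesion or new bone-scan uptake. Rule 7 uses the PSA fall after targeted treatment.

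False-positive rule 2 is a residual category. It applies if "positive bone lesions do not meet the criteria for true positive findings, and appropriate correlative and follow-up imaging was acquired".

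Two other places deal with mimics. Section 1.1.8.2 D), in the miTNM reporting framework, states: "PSMA-positive pitfalls such post-traumatic rib uptake, or non-prostate cancer related primary malignancies have to be ruled out". Section 1.1.8.4 B) makes a biopsied bone lesion false positive "If pathology demonstrates an alternative diagnoses that is known to be PSMA positive", with renal cell metastases and Paget's disease as examples. Section 1.1.8.4 C) ranks pathology above imaging and lets investigators depart from the criteria in individual cases, with a record. PPV per patient and per region is a secondary endpoint (1.1.3.3), reported with Wilson 95% intervals and without a target (1.1.9.5).

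**The concern.** PPV is meant to count how often a positive PET reading is wrong, so the reference standard has to be able to call a benign or non-prostate lesion false positive. Rules 2 and 3 accept a finding because of where it is, whatever it looks like. Rule 1 names one appearance, sclerosis, but excludes no benign cause. Once any of the three is met, false-positive rule 2 cannot apply.

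The classification of one and the same lesion then depends on whether it was biopsied. A renal cell metastasis in bone is false positive if pathology identifies it. If it is only imaged and appears as a lesion on the baseline MRI, it is true positive as the rules are written. Bone is one of the four regions in the per-region analysis, and one true-positive region is normally enough to make the patient true positive, so the misclassification can reach both PPV estimates.

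**Working it through.** **Can the rules as written produce the misclassification?** Take a PET-positive bone lesion that is a mimic, was not biopsied, and has a bone-scan or MRI correlate at baseline.

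1. Rule 2 or 3 is met, because neither has a condition on appearance or cause.
2. False-positive rule 2 needs every true-positive rule to fail, so it does not apply.
3. The pathology rule in 1.1.8.4 B) does not apply without tissue, and biopsy is sought only where feasible.
4. At region level, an imaging true positive overrides imaging false positives in the same region (1.1.8.4 C).

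The lesion and its region are true positive unless an investigator records a deviation. Rules 4 to 6 do not share this route: a mimic already visible at baseline is not new or developing.

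**Size.** The documents give no expected bone PPV, mimic rate or correlate rate, so there is no stated figure to reproduce. All values of p, m and s below are assumptions.

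- p = true bone PPV
- m = share of PET-positive mimics that meet a true-positive rule
- s = share of true metastases that meet a true-positive rule

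With all lesions evaluable and none biopsied:

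reported PPV = p × s + (1 − p) × m

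*Upward component alone (s = 1).* The shift is (1 − p) × m. At p = 0.80:

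| m | Reported PPV | Shift |
|---|---|---|
| 0.25 | 0.80 + 0.20 × 0.25 = 0.85 | +0.05 |
| 0.50 | 0.80 + 0.20 × 0.50 = 0.90 | +0.10 |
| 0.75 | 0.80 + 0.20 × 0.75 = 0.95 | +0.15 |

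Over p = 0.60 to 0.90 and m = 0.25 to 0.75, the shift runs from 0.10 × 0.25 = +0.025 to 0.40 × 0.75 = +0.30.

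*Net effect (s < 1).* Under false-positive rule 2, a true metastasis that meets no true-positive rule becomes false positive if adequate imaging was done. Section 1.1.1 calls CT, MRI and bone scan insensitive, without a figure. At p = 0.80:

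| s | p × s | m = 0.25 | m = 0.50 | m = 0.75 |
|---|---|---|---|---|
| 1.00 | 0.80 | 0.85 | 0.90 | 0.95 |
| 0.90 | 0.72 | 0.77 | 0.82 | 0.87 |
| 0.80 | 0.64 | 0.69 | 0.74 | 0.79 |

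Reported PPV exceeds the truth only if m > p × (1 − s)/(1 − p). At p = 0.80 that threshold is 0.08/0.20 = 0.40 for s = 0.90, and 0.16/0.20 = 0.80 for s = 0.80.

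*Against sampling error.* The abstract at the front of the document reports skeletal metastasis on PET in 7 of 41 patients. If that carried over to 400 patients, about 400 × 7/41 = 68 would be bone-positive. With 68 evaluable, the Wilson 95% interval is 0.684 to 0.873 at a true PPV of 0.80 (54/68) and 0.802 to 0.949 at a reported 0.90 (61/68). A 10-point shift would put the whole interval just above the true value, and nothing in the interval would reveal it.

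**The case against.** The strongest reply is that the plan has safeguards. Pitfalls have to be ruled out, pathology takes precedence, and section 1.1.8.4 C) calls the criteria a guide from which investigators may depart. A reader might infer that every such mimic is counted as a confirmed metastasis; the documents do not support that, and *can be counted* is as far as they go. But the safeguards do not close the gap. The instruction on pitfalls belongs to PET reporting, whereas the reference standard has to judge lesions that were still read as positive. The pathology rule needs tissue. Recorded deviation is discretion case by case, not a prespecified rule.

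A reader might also infer that bone PPV is inflated overall. That is not shown. The second table has values below the true 80% as well as above it, and the inputs that decide between them are not in the documents. This part of the objection stands. It does not justify the rule, because an opposing error of unknown size leaves PPV wrong by an unknown amount.

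The documents do not say how often the named mimics show on bone scan or MRI, so how much this matters in practice is unknown. That is why m is given as a range.

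Finally, the bone section says that lesions meeting neither set of criteria are unevaluable for the primary endpoint, from which a reader might infer that the primary endpoint is at risk. It is not: section 1.1.3.3 defines that endpoint as management change, and neither it nor the sample size uses these rules.

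**Conclusion.** The point holds for bone rules 2 and 3 and, in a similar way, for rule 1; it does not extend to rules 4 to 6. As written, a named mimic that was read PET-positive, not biopsied and not handled as a deviation can be scored true positive, although an alternative diagnosis on pathology would make it false positive. The upward component is (1 − p) × m, or 5 to 15 points at p = 80% and m = 25% to 75%. Both values are assumed, with all lesions evaluable and none biopsied. The sign of the total error in bone PPV is not established.

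Per-patient PPV changes only when the mimic is the patient's sole true-positive finding and no region is false positive on pathology; its size cannot be estimated from the documents. This is a worthwhile correction to a secondary endpoint.

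**What to change.** Amend the bone rules in section 1.1.8.4 as follows:

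- **Rules 1 to 3:** count the baseline correlate as true positive only if its imaging report describes it as suspicious for or consistent with metastasis.
- **Benign or alternative diagnosis:** a correlate reported as such does not satisfy rules 1 to 3. The lesion is false positive unless pathology or one of rules 4 to 7 confirms metastasis. Keeping that exception matters, because a blanket override would let one benign reading defeat positive pathology, later sclerosis or a PSA response.
- **Equivocal correlates only:** the lesion is unevaluable. Without this sentence, false-positive rule 2 would absorb it.
- **Sensitivity analysis:** report bone PPV also under the rules as they now stand, so that the effect of the change is visible.

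The change is one of wording and uses existing imaging reports. The costs are a somewhat lower bone PPV, more unevaluable lesions, and some work to map local report wording to the certainty terms. Table 10 belongs to the PET reporting framework, and follow-up imaging is read locally, so those reports may not use its terms. The change does not remove the opposite error, in which true metastases without any correlate are scored false positive; that should be acknowledged when bone PPV is reported.
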